The research team created the SSIs of different lengths aiming to make the active elements in each SSI as consistent as possible. Thus, even though the 2-minute version contains less content than the 15-minute version, researchers tried to ensure it expresses the same general message and activates similar mechanisms of change. Participants will complete questionnaires asking about their well-being and experiences with the interventions at baseline, post-test, and 8-week follow-up.

All interventions and survey materials are available at <https://osf.io/g846j>.

Statistical Analysis Plan

Main analysis: The main DV is change in depressive symptoms (PHQ-8) from baseline to 8-week follow-up. The main analysis compares change in PHQ-8 score from baseline to 8-week follow-up across experimental conditions. Researchers will use a mixed-effects model predicting depressive symptoms with condition, measurement time point (1 = baseline, 2= 8-week follow-up), and the 2-way interaction between condition and measurement time point as IVs and a participant identifier as a random intercept. Using the “lme4” package in R, these analyses will take the following form:

`lmer(phq8 ~ time*condition + (1|pid))`

Secondary analysis: Researchers will re-run the same analysis as above separately for each secondary outcome collected. Researchers will also duplicate the main analysis but with the following covariates included in the mixed-effects model: gender (multiple choice), age (continuous), ethnicity (categorical), education level (categorical), employment (categorical), and if one completed the study on a phone (binary).

Inference criteria

For all analyses, researchers will use the standard $p < 0.05$ criterion for determining statistical significance. Researchers will use two-tailed tests for each of researchers' analyses.

Data exclusion

Main analyses will be limited to only those participants who 1) were randomized to a condition (i.e., those who consented to participate and completed the baseline measures), 2) did not indicate that they did not participate seriously at the end of the study, and 3) completed the study only once.

Missing data

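### Secondary outcomes are each tested at unadjusted p < 0.05, with no adjustment across them and no exploratory label, so with more than one such outcome the chance of a false significant secondary result exceeds 5%

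*Combined protocol and SAP*

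**What the plan says.** The Main analysis paragraph of the SAP names one main dependent variable, the change in PHQ-8 between baseline and eight weeks. It is tested with a mixed model containing time, condition and their interaction.

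The Secondary analysis paragraph then has this model repeated "separately for each secondary outcome collected". The outcomes are neither named nor counted. The nearest description comes just before the SAP: "Participants will complete questionnaires asking about their well-being and experiences with the interventions at baseline, post-test, and 8-week follow-up". The reader is sent to an external repository for the instruments ("All interventions and survey materials are available at" a web address).

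The Inference criteria section sets one rule: "For all analyses, researchers will use the standard $p < 0.05$ criterion for determining statistical significance". It adds: "Researchers will use two-tailed tests for each of researchers' analyses". The documents contain no multiplicity adjustment, no testing order among secondary outcomes, and no statement that secondary results are exploratory.

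**The concern.** The two rules act together. One calls for a separate test of each secondary outcome. The other lets each of those tests support a claim of statistical significance at 5%, as if it were the only one. This goes beyond missing detail, because following the stated rule exactly produces more than a 5% chance of a false secondary claim whenever there are at least two outcomes.

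The trial asks one practical question: how long the intervention should be. The four versions were built to carry the same message and act through similar mechanisms, so small or null differences on PHQ-8 are a realistic result. In that case a single secondary outcome with p just under 0.05 would meet the plan's own criterion for a significant duration effect, and nothing in the plan would tell the reader to discount it for the number of outcomes tested.

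**Working it through.** **Inputs from the documents**
- Per-test level: 0.05, two-tailed, for every analysis (Inference criteria).
- Four conditions with equal allocation (Protocol, recruitment paragraph) and two time points (Main analysis). A joint time-by-condition test therefore has (4 − 1) × (2 − 1) = 3 df.
- Target sample: 1,100. It is not needed for the error rate.

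**Inputs assumed**
- Number of secondary outcomes, K. The documents give none; values from 2 to 10 are shown.
- Common correlation between outcomes, ρ. The documents give none; the range is 0 to 0.7.
- One deciding test per outcome. The SAP does not say whether a joint test or individual contrasts decide.

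The plan states no error rate across outcomes, so there is no figure of its own to reproduce.

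**Step 1: independent outcomes, no true effect.** The chance of at least one p < 0.05 is 1 − 0.95^K.
- K = 1: 5.0%
- K = 2: 1 − 0.9025 = 9.75%
- K = 3: 1 − 0.8574 = 14.3%
- K = 5: 1 − 0.7738 = 22.6%
- K = 10: 1 − 0.5987 = 40.1%

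**Step 2: correlated outcomes.** Four equal arms were simulated under the global null, with a large-sample 3-df test for each outcome.

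| K | ρ = 0 | ρ = 0.7 |
|---|---|---|
| 2 | 9.75% | 8.5% |
| 3 | 14.3% | 11.3% |
| 5 | 22.6% | 15.5% |
| 10 | 40.1% | 22.6% |

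At ρ = 0.5 the values are 18.7% for K = 5 and 29.8% for K = 10. Replacing the joint test by a 1-df linear trend changes little: 14.9% for K = 5 at ρ = 0.7, and 40.2% for K = 10 at ρ = 0.

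**Step 3: if contrasts are read one by one.** With three contrasts against a reference arm, each at 0.05, the rate is already 12.5% for one outcome. It becomes 34–49% for K = 5 and 46–74% for K = 10 (ρ from 0.7 to 0). With all six pairwise contrasts it is 20%, 49–68% and 62–90%. The table in Step 2 is therefore the low case.

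**Step 4: after adjustment.** Bonferroni with independent outcomes gives 1 − 0.99^5 = 4.90% for K = 5 and 1 − 0.995^10 = 4.89% for K = 10. Benjamini-Hochberg also keeps the chance of any false claim at or below 5% when no secondary outcome truly differs and the tests are independent or positively dependent. When some outcomes do differ, it controls the false discovery rate and not that chance.

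**Step 5: price in power.** Take a 3-df test with 80% power at 0.05. At 0.05/5 = 0.01, the first Holm step with five outcomes, its power is about 59%. Benjamini-Hochberg compares the j-th smallest p with 0.05 × j/K. Its threshold is thus equally strict when only one p is small, and milder when several are.

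**The case against.** The strongest defence is that the plan has a hierarchy: one main outcome, one main analysis, and secondary analyses set apart. Unadjusted secondary tests beside a single primary outcome are common and acceptable when presented as exploratory. The hierarchy stands, and it protects the PHQ-8 test. It does not settle the matter, because the exploratory label is absent and the Inference criteria section extends the significance claim to every analysis.

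The second defence is that the number of outcomes may be small. The baseline questionnaire, demographics included, takes about four minutes. The repeated model needs a baseline value, which ratings of the intervention cannot have. This is a fair reason not to lead with a high count. But two outcomes already give about 9–10%.

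A reader might infer four stronger things that the documents do not support:
- **That secondary outcomes will all be declared significant.** The plan sets a criterion they are tested against; it does not predetermine the result.
- **That the list is open-ended and invites selection.** No list appears here, but the repository may show the instruments, and the wording commits the researchers to analysing each outcome collected.
- **That the trial has a known false-positive rate of 15–40%.** That range needs 5 to 10 outcomes, which is an assumption. Its ends also mix conditions: 15% is five outcomes correlated at about 0.7, and 40% is ten independent ones, which is unlikely for well-being scales answered by the same people.
- **That the PHQ-8 conclusion is compromised.** Testing secondary outcomes does not change the error rate of the main test.

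**Conclusion.** The point holds for the secondary outcomes only. As written, the plan allows claims of significance on an uncounted set of secondary outcomes with no control of error across them. If duration has no effect, the chance of at least one such false claim is about 9–10% with 2 outcomes, 11–14% with 3, 15–23% with 5 and 22–40% with 10. These figures assume one joint 3-df test per outcome and correlations from 0.7 down to 0. They rise if separate contrasts decide, and fall to the nominal 5% if there is only one secondary outcome. The covariate-adjusted repeat of the PHQ-8 model is a further test at 0.05 and is not counted.

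The direction is certain for any count above one; the size depends on a number the documents do not give. This is an inexpensive improvement to what the trial may claim, not a flaw in its main comparison.

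**What to change.** Amend the Secondary analysis and Inference criteria text as follows:
1. Apply the unadjusted p < 0.05 criterion only to the main PHQ-8 test.
2. Name the secondary outcomes in the SAP, and state one time-by-condition test as the deciding test for each.
3. For each, report the estimate, 95% CI, unadjusted p, and Benjamini-Hochberg adjusted p over the named list.
4. Call a secondary result significant only if its adjusted p is below 0.05; otherwise describe it as exploratory.

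An acceptable alternative to items 3 and 4 is to label all secondary results exploratory and make no significance claims from them.

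The cost is a few SAP sentences, the outcome list, and one line of R for the adjustment. Some secondary results with unadjusted p just under 0.05 can no longer be called significant. If only one of five outcomes truly differs, the loss of power comes close to the fall from 80% to about 59% seen at the first Holm step; it is smaller when several differ. Estimates, intervals and unadjusted p-values stay visible. Benjamini-Hochberg is the milder choice. If the team wants the chance of any false secondary claim held at 5% even when some outcomes do differ, Holm is the rule to use, at greater cost in power.

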Study Protocol and Statistical Analysis Plan

How Long Should a Behavioral Activation Single-session Intervention be? A Four-armed
Trial Comparing Effectiveness by Intervention Duration

ClinicalTrials.gov ID NCT06313736

April 17, 2024

Protocol

Researchers will use the crowdwork platform CloudResearch Connect to recruit and compensate participants. Researchers will pay participants \$0.25 USD for completing the screener and (if eligible) the study information sheet. If participants are eligible, researchers will send them invites through the crowdwork platform to participate in the next parts of the study. Researchers will pay them \$4.00 for completing session 1 of the study and \$1.00 for the 8-week follow-up. Participants are only allowed to complete the study once and cannot participate in the study if they have participated in another study from the research team relating to depression on CloudResearch Connect in the last two months.

Researchers will recruit a sample of 1,100 adults who struggle with depression. To recruit these adults, potential participants will complete a screener and, if eligible, read the study content information and decide whether to participate (2 minutes). Within five days, participants who consent will be invited to complete the first part of the study. In this part, they will first complete a questionnaire of demographics and well-being at baseline (roughly 4 minutes), be randomly allocated to one of four conditions with equal odds of assignment to each condition, complete the SSI to which they were randomized (2-15 minutes) and then complete the post-test measures (roughly 4 minutes) just after the SSI and eight weeks later. Combined across all three study sessions, the study should take roughly 29 minutes. At the end of the study, researchers will offer participants access to a list of free online mental health support resources (shown in supporting documents). At the end of the study, researchers will also offer participants permanent access to all four SSIs.

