Based on researchers' previous work on Cloudresearch Connect, researchers do not foresee a great deal of missing data or differential dropout. Although researchers will take efforts to avoid missing data (e.g., a financial incentive for completing the study and reminder emails), it is not necessary to impute missing data before performing a longitudinal mixed-model analysis (Twisk et al., 2013). Participants with missing data at some assessments will be included in the analysis and results will be modeled on the basis of the available data.

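### As worded, the covariate-adjusted secondary analysis repeats the unadjusted time-by-condition result: exactly with complete follow-up, and nearly so under the dropout the SAP expects

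*Combined protocol and SAP*

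**What the plan says.** The Main analysis paragraph of the SAP fits PHQ-8 at two time points, baseline and 8 weeks, with the call "lmer(phq8 ~ time*condition + (1|pid" (closing brackets omitted here). The effect of interest is the time-by-condition interaction.

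The Secondary analysis paragraph adds: "Researchers will also duplicate the main analysis but with the following covariates included in the mixed-effects model". Six covariates follow: gender, age, ethnicity, education, employment, and "if one completed the study on a phone (binary"). No adjusted formula is written.

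The Protocol section places the demographics in session 1, where "they will first complete a questionnaire of demographics and well-being at baseline", so each has one value per person. Under Missing data, "researchers do not foresee a great deal of missing data or differential dropout", and "Participants with missing data at some assessments will be included in the analysis". Under Data exclusion, everyone analysed has completed the baseline measures, so missing outcome data means a missing 8-week score.

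**The concern.** A reader expects an adjusted analysis to show whether chance imbalance in the covariates accounts for some of the difference in change between arms. Covariates added as main effects describe differences in the level of PHQ-8, not in its change. The interaction compares changes, so a covariate that is constant within a person has almost nothing to act on.

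This is the only covariate-adjusted analysis in the SAP. A report that the result held after adjustment for six covariates would present something close to an algebraic identity as support for the main finding.

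**Working it through.** **Inputs from the documents.** 1,100 participants, four arms with equal odds (1,100 / 4 = 275 per arm), two time points, a random intercept, and two-sided tests at 0.05. The documents give no SD, correlation, covariate strength or dropout percentage, so those values below are assumptions. The plan has no figure of its own on this point to reproduce.

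**Step 1: algebra with complete pairs.** For person *i* in condition *c*, with covariates x:

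- baseline: Y1 = μ + α_c + x′β + b + e1
- 8 weeks: Y2 = μ + τ + α_c + γ_c + x′β + b + e2

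Difference: D = Y2 − Y1 = τ + γ_c + (e2 − e1). Both x′β and b cancel.

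Sum: S = Y1 + Y2 = 2μ + τ + 2α_c + γ_c + 2x′β + 2b + (e1 + e2).

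D and S are independent. Because α_c is free, S carries no information about γ_c. The interaction is therefore the difference in mean D between arms, with or without x. Under REML (the lme4 default) the residual variance σ² also comes from D alone, so SE(γ) = √(4σ²/n) with n per arm, and it too is unchanged.

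This requires covariates that are constant within a person, no missing covariate values and a positive estimated intercept variance. It does not depend on whether x predicts change.

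**Step 2: numerical check, complete data.**

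- One simulated trial of 1,100: contrasts 0.3055, −0.3233 and −0.3181, SE 0.3865 and 3-df Wald 3.626, the same without and with covariate main effects. The fitted σ² was 10.2687, and √(4 × 10.2687 / 275) = 0.3865, as the formula says. With covariate-by-time terms: 0.3619, −0.3326 and −0.3055, SEs 0.388 to 0.392, Wald 4.138.
- A second trial, fitted with different software: 0.224626, −0.806650 and −0.807081, SE 0.38411, again the same in both models. With covariate-by-time terms: 0.112, −0.773 and −0.800.

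**Step 3: missing follow-ups.** Baseline-only records break the separation of D and S, so the estimate can move. Two sets of simulations measure by how much, each with 15 covariate columns (an assumed number of categories):

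- Set A: SD 4.8, correlation 0.5–0.6, covariates explaining 5–20% of level variance and 0–10% of change variance; 400 trials per setting. By the formula, complete-data SEs run from √(4 × 4.8² × 0.4 / 275) = 0.37 to √(4 × 4.8² × 0.5 / 275) = 0.41. Across all settings they were 0.37–0.45.
- Set B: SD 5, correlation 0.6, covariates explaining 5% or 25% of PHQ-8 variance, random dropout; 100 trials per setting.

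Shift in the contrasts from adding main effects:

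| Dropout | A: mean shift, points | A: largest single shift | B: mean shift in SEs (5% / 25%) | B: significance changed (5% / 25%) |
|---|---|---|---|---|
| 0% | 0.0000 | – | 0.000 / 0.000 | 0/100, 0/100 |
| 5% | 0.008–0.020 | 0.09 | 0.022 / 0.051 | 0/100, 4/100 |
| 10% | 0.012–0.029 | 0.13 | 0.028 / 0.069 | 0/100, 5/100 |
| 20% | 0.017–0.044 | 0.22 | 0.040 / 0.101 | 1/100, 2/100 |

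In set A the SE never changed by more than 0.006.

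**Step 4: where main effects do act.** With covariate-related dropout concentrated in one arm, that arm's contrast moved on average 0.046, 0.085 and 0.148 points at 5%, 10% and 20% dropout (set A). In set B, with about 20% dropout differing by arm and covariates, the mean shift was 0.17 or 0.41 SE, and significance changed in 8/100 or 22/100 trials.

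**Step 5: phone use.** If it is recorded per session and 20% of participants switch device, the contrasts move by 0.021 or 0.053 SE on average even with complete follow-up (set B).

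**Step 6: covariate-by-time terms, complete data.** They moved the contrasts by 0.034–0.110 points on average (set A). The ratio of their SE to the unadjusted SE was 1.007, 0.982 and 0.956 when the covariates explained 0%, 5% and 10% of change variance.

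**The case against.** The strongest reply concedes the algebra and disputes its weight.

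- The SAP does not rule out covariate-by-time terms, so strictly the defect is an unwritten formula. That stands, but main effects are the plainer reading: the paragraph above spells out the time-by-condition interaction in words and code, and no other interaction is mentioned. If interactions were meant, the same line of text settles it.
- The SAP expects little missing data, not none, and a main-effects model responds to covariate-related dropout that differs by arm. That also stands, and the model is not redundant in every case. A borderline p-value can cross 0.05 at 5–10% random dropout as well, though in set B this happened only when the covariates explained 25% of the variance. Such movement comes from baseline-only records, not from adjusting change for covariate imbalance.
- The SAP does not call this analysis a robustness check and ties no decision to it. True; the harm lies in how agreement would be read.
- The remedy changes little: 0.034/0.41 to 0.110/0.37 is about 0.1 to 0.3 SE. Randomisation already guards against systematic imbalance, and nothing in the documents shows that these covariates predict change. In set B, where they did not, covariate-by-time terms still moved the contrasts by 0.09–0.10 SE, which is estimation noise. So the case for them is that they can adjust change, not that they will improve precision.
- Phone use is worded at study level, which suggests one value per person. That is reasonable, but the study has several sessions and the SAP does not say which one defines it.

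**Conclusion.** The concern holds. Read as main effects, the adjusted model cannot alter the time-by-condition estimate, SE or test when follow-up is complete. This is algebra and rests on no assumed SD, correlation or covariate strength, only on the conditions in Step 1.

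Under low dropout similar across arms, the average shift is at most 0.029 points at 10% missing, or 0.029/0.37 ≈ 0.08 SE; that size does depend on the assumed parameters. Dropout that differs by arm and covariates is the exception. The consequence is limited to a secondary analysis, but the correction is cheap and should be made.

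**What to change.** Write the adjusted model into the Secondary analysis paragraph so that the covariates act on change and all available records are kept, as the Missing data section plans:

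`phq8 ~ time*condition + time*(gender + age + ethnicity + education + employment + phone) + (1|pid)`

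Define phone use once, from session 1 before randomisation, and say how missing covariate values are handled, since they would drop records. If a main-effects version is kept, state that its agreement with the main analysis is not evidence of robustness.

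The cost is one line of text and no new data. The model gains about 15 parameters (the number depends on category counts that the documents do not give), and the SE is about 0.7% larger if the covariates do not predict change.

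An optional addition is a regression of 8-week PHQ-8 on condition, baseline PHQ-8 and the same covariates. With complete data its SE was 0.31–0.35 against 0.37–0.41 for the change model (assumed parameters), a comparison that includes the adjustment for baseline PHQ-8. It excludes participants without an 8-week score unless imputation is added, which departs from the Missing data section, so their handling must be stated.

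### The main analysis drops randomised participants on the strength of a seriousness answer given after the intervention, and no planned analysis shows what that does

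*Combined protocol and SAP*

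**What the plan says.** The Protocol section gives the order of events. Participants complete the baseline questionnaire and are then to "be randomly allocated to one of four conditions with equal odds of assignment to each condition". Next they "complete the SSI to which they were randomized (2-15 minutes" and answer the post-test measures, with a further assessment eight weeks later.

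Under Main analysis, the SAP states that "The main analysis compares change in PHQ-8 score from baseline to 8-week follow-up across experimental conditions". The Data exclusion section then restricts the set: "Main analyses will be limited to only those participants who 1) were randomized to a condition", who also "did not indicate that they did not participate seriously at the end of the study" (criterion 2), and who completed the study only once (criterion 3).

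Three other provisions bear on the point:

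- **Secondary analysis.** The same model is run for each secondary outcome, and "Researchers will also duplicate the main analysis but with the following covariates included in the mixed-effects model". No different analysis population is named for either.
- **Missing data.** "Participants with missing data at some assessments will be included in the analysis". This covers absent assessments, not people removed by rule.
- **Repeat entry.** The Protocol says "Participants are only allowed to complete the study once". Criterion 3 enforces this rule and is not in dispute here.

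The documents do not say at which session the seriousness question is asked, how it is worded, or how many people are expected to be excluded.

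**The concern.** Criterion 2 selects on something measured after randomisation and after exposure. The arms differ in length, and a participant's view of how seriously they took part could plausibly depend on whether the task lasted 2 or 15 minutes. If so, different kinds of people are removed from different arms, and the balance that randomisation provides is lost in the comparison the trial exists to make. A difference in PHQ-8 change between lengths, or the absence of one, could then partly reflect who was removed.

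The rule may also act unevenly. Someone who leaves before the question is asked cannot give the excluding answer and stays in under the available-data rule, while someone who stays and answers candidly is taken out.

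Fixing the rule in advance limits the analyst's discretion, but it does not make the answer independent of the arm.

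**Working it through.** **Text check.** The order is baseline, allocation, assigned session, post-test, 8-week follow-up. Whether the end of the study means the end of the first session or the 8-week follow-up, the answer comes after the assigned length has been delivered. The covariate-adjusted rerun does not lift the exclusion. Even if the secondary analyses were read as unrestricted, that rerun would change covariates and population together and could not isolate the effect of the rule.

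**Size.** The plan contains no figure to reproduce, so this is an illustration.

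- From the documents: 1,100 / 4 = 275 per arm; two-sided 5% level.
- Assumed: PHQ-8 SD 5; baseline-to-follow-up correlation 0.6; D, the improvement of retained minus excluded people, 2 to 4 points; all exclusion rates.

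Variance of the change score = 2 × 5² × (1 − 0.6) = 20.

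SE of a pairwise difference in change = √(20 × 2/275) = 0.381 points.

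Bias in the 15- versus 2-minute contrast = p₁₅D₁₅ − p₂D₂, where p is the share excluded. With the same D in both arms this is (p₁₅ − p₂) × D.

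Type I error = Φ(−1.96 + bias/SE) + Φ(−1.96 − bias/SE).

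For the joint 3-df test, rates rise in even steps over the four arms, and the non-centrality is 275 × Σ(bᵢ − b̄)²/20 with bᵢ = pᵢD.

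| Excluded, 2 vs 15 min | Bias (points), D = 2 to 4 | Bias/SE | Type I, pairwise | Non-centrality | Type I, joint |
|---|---|---|---|---|---|
| 1% vs 3% | 0.04–0.08 | 0.105–0.210 | 5.1–5.5% | 0.012–0.049 | 5.1–5.3% |
| 2% vs 6% | 0.08–0.16 | 0.210–0.420 | 5.5–7.0% | 0.049–0.196 | 5.3–6.2% |
| 2% vs 10% | 0.16–0.32 | 0.420–0.839 | 7.0–13.4% | 0.196–0.782 | 6.2–10.0% |

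For scale, the pairwise difference detectable with 80% power under these assumptions is (1.960 + 0.842) × 0.381 = 1.07 points. A bias of 0.32 is 30% of that, and 0.08 is 7%.

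**Equal rates do not guarantee safety.** With 5% excluded in both arms:

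- D of 2 in one arm and 4 in the other: bias 0.05 × (4 − 2) = 0.10, bias/SE 0.262, type I error 5.8%.
- D of −2 and +2: bias 0.05 × 4 = 0.20, bias/SE 0.524, type I error 8.2%.
- The same D in both arms: bias zero.

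**Sensitivity to the correlation.** Over 0.4 to 0.8, the pairwise type I error spans 5.3–9.1% at 2% versus 6%, and 6.3% to about 22% at 2% versus 10%.

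**The case against.** The best defence is that this is a pre-specified data-quality filter for unsupervised crowdwork. If the item mainly detects careless questionnaire answers, part of D is measurement error. Keeping those people then has its own cost: with 6% answering without content (assumed), a true length effect shrinks by roughly 6%, and carelessness that differs by arm would bias the full set instead. The item's wording and timing are not in the documents. If it is asked at 8 weeks, an effect of session length on the answer is less obvious.

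The larger error rates also need strong assumptions: a fivefold gap in exclusion between arms, or differences of opposite sign. A D of 4 points is about 0.9 SD of the assumed change score (√20 = 4.47). The SE of 0.381 uses all 275 per arm; with the retained numbers, the 13.4% becomes 12.8%. Finally, a plan this short may simply leave a routine participant-flow count unstated.

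Much of this stands as a caution about size. It does not answer the structural point. The answer follows exposure on either reading of its timing, the documents give no rate from which to argue that the effect is small, and as planned no reader could check. The SAP's expectation of little differential dropout concerns missing data, not this exclusion. The attenuation argument is a good reason to run the filtered analysis as well, but not to run it alone.

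**Conclusion.** The concern holds and should be fixed. The text settles that randomised participants are removed from the main PHQ-8 comparison by a variable measured after exposure, and that nothing planned reveals the consequence. The direction and size of any bias are unknown.

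Under the assumptions above, the effect runs from negligible (few exclusions, similar rates and similar outcome differences across arms) to a pairwise type I error of 13.4%, or 10.0% for the joint test, when exclusion is both strongly differential by length and strongly related to outcome. Every input except 275 per arm and the 5% level is assumed, so these figures show what could happen and are not forecasts.

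**What to change.** In the Data exclusion section:

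1. Remove criterion 2 from the definition of the main analysis set. Keep criteria 1 and 3, and analyse participants in the condition to which they were assigned.
2. Rerun the same mixed model with the seriousness exclusion as a named sensitivity analysis.
3. Report the number excluded by arm, and state when the seriousness question is asked.

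If the team prefers to keep the filtered set as primary, running the model both ways with counts by arm is the minimum that lets a reader judge the effect.

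The work is SAP wording and one more run of the same model. The cost in precision is small. With a share p careless, whose change scores have k times the variance (both assumed), the SE with everyone kept is √(2 × 20 × (1 − p + kp)/275), against √(2 × 20/(275(1 − p))) with them removed.

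- p = 6%, k = 2: 0.393 either way, because the extra participants offset the noise.
- p = 10%, k = 3: 0.418 against 0.402, about 4% wider.

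These SEs leave out the attenuation noted above, which the sensitivity analysis would help to show.
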